12.1.2 Secondary Objectives

Secondary objectives include health-related quality of life (HRQOL) measures including: 1) the Expanded Prostate Cancer Index Composite (EPIC) short form questionnaire, 2) AUA symptom survey. These will be assessed at baseline and first follow-up (approximately 1 month, or 30 days, status post end of treatment). Follow-up measures as well as changes from baseline to follow-up will be studied.

12.1.3 Correlative Study Objectives

Microbiome and labs will be collected for exploratory analyses to see how radiation impacts the host microbiome and peripheral immune correlates found in blood. This is an exploratory analysis.

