5 STUDY PROCEDURES

| | Pre-Study | Fx 1 | Fx2 | Fx 3 | Fx 4 | Fx 5* | Post-RT Visit (3-6 month s/p RT) |
|--|-----------|------|-----|------|------|-------|----------------------------------|
| Informed consent | X | | | | | | |
| Demographics | X | | | | | | |
| PSA | X | | | | | | X |
| Acute/Late Toxicity Assessment (CTCAE) | X | | | | | X | X |
| EPIC-26, AUA | X | | | | | | X |
| Imaging: Planning CT/MR; | X | | | | | | |
| Optional: blood draw and microbiome sample | X | | | | | X | X |

**at physician's discretion, lymph nodes may be targeted in the radiation field, either in 5 fractions or over 5-6 weeks using standard fractionation*

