5.2 Imaging Studies

Patients enrolling on the protocol will be treated as follows. Placement of a rectal spacer is optional; patients who refuse or decline a rectal spacer will have the option to be treated with an endorectal balloon (ERB). Patients will be instructed to undergo a Fleet enema prior to planning CT and prior to each SBRT treatment.

All patients will be sent for a pelvic MRI for treatment planning purposes, or have an MR on the Viewray machine. This should ideally be done within 1-2 weeks of the treatment planning CT. The ideal MRI, if not done on the Viewray, will be 3Tesla and in a position similar to treatment position, without use of an endorectal coil which can distort the prostate shape. If rectal spacer is

placed, the treatment planning MRI should be performed after the spacer placement.

Treatment planning CT will be performed with vac loc immobilization. Patients will be advised to drink 1-2 cups of water 1 hour prior to the CT simulation to allow for a comfortably full bladder, if tolerated. A rectal catheter will be utilized to dispel any excess bowel gas, if necessary. A urethral catheter to delineate the urethra at time of simulation can be considered if it is difficult to visualize the urethra on initial MRI. Oral contrast may be administered as per standard protocol if lymph nodes are being targeted.

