9 CORRELATIVE/SPECIAL STUDIES

9.1 Correlative Study: Blood draws for immune correlates and microbiome collection

Patients will have the option of having a blood draw prior to, at the completion of radiation and at 3-6 months post treatment follow up. They will also have the option of providing a stool sample for microbiome analysis at baseline, end of completion and 3-6 month follow up. This is an exploratory study where specimens will be stored for future analyses.

Blood Sample Collection and Procedure

Blood samples (40-ml) will be collected in heparinized “Green Top” tubes (for PBMC and plasma isolation) and processed within 4 h of sample receipt. The PBMC will be isolated using a 1.077 g/ml Ficoll layer to enrich the leukocytes and remove the dead cells and any red cells, and cryopreserved in 10% DMSO, 90% human AB serum at 10×10^6 cells/vial and stored in liquid nitrogen for batch analysis. Plasma will also be aliquoted and stored at -80^0C for batch analysis. We anticipate analyses of T cell subsets and neutrophil/lymphocyte ratios, as well as cytokine measurement and proliferation analyses (all markers of peripheral immune correlates to assess status over time) once funding is secured.

Microbiome collection

Collection of Specimen(s): Patients will be provided with a stool collection container and be instructed on providing a specimen appropriately, which can be done from home or in the clinic.

Handling of Specimens(s): Samples received will be promptly frozen at 20 degrees C, and transferred within the next week to a -80 degree freezer or liquid nitrogen for long-term storage. DNA extractions and 16sRNA analysis will be performed once all samples are collected.

The microbial DNA will be isolated and used to provide DNA sequence information. We will perform taxonomic characterization of bacteria (using 16S rRNA). Prokaryotic diversity will be screened using massively parallel DNA sequencing, exploiting a multiplexing technique to generate 16S rRNA sequence tags, followed by analyses (statistical, clustering, and phylogenetic) to estimate the distribution of phylotypes, differential abundance, and the relative contributions between phylotypes and community dissimilarities to the overall diversity in individuals.

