We will examine whether there are metagenome sequence content changes during radiation treatment, and study whether differences in gene content indicate differences in functional pathways between the normal and irradiated microbiome using pathway analysis.

Samples will be collected by the research team and the samples will be stored in -80C freezer in [name] lab until sample analysis.

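### The microbiome change from baseline to end of radiation reflects radiation plus repeated enemas, so it cannot be read as the effect of radiation alone (minor)

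*Combined protocol and SAP*

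**What the plan says.** Section 12.1.3 (Correlative Study Objectives) describes "exploratory analyses to see how radiation impacts the host microbiome" and on peripheral immune markers, and calls the work exploratory. Section 9.1 offers patients the option of "providing a stool sample for microbiome analysis at baseline, end of completion and 3-6 month follow up"; collection is something "which can be done from home or in the clinic". It then states two analyses: "We will examine whether there are metagenome sequence content changes during radiation treatment", and a study of "differences in functional pathways between the normal and irradiated microbiome".

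The schedule in section 5 marks the optional blood and microbiome sample at three points: Pre-Study, Fx 5 and the post-RT visit at 3-6 months. The schema and section 9.1 describe the middle sample as end of radiation.

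Section 5.2 opens with "Patients enrolling on the protocol will be treated as follows" and continues: "Patients will be instructed to undergo a Fleet enema prior to planning CT and prior to each SBRT treatment". In that paragraph only the rectal spacer and the balloon are optional. The Protocol Summary describes a single-arm study.

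No section times the stool sample relative to an enema, asks for the time of the last enema, or mentions the enema as an exposure that accompanies the radiation.

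**The concern.** An enema acts on the compartment that the stool sample is meant to represent. If enemas are given alongside the fractions and the on-treatment sample is taken in the middle of that course, a change from baseline has two candidate causes, and the plan names only one. A shift that came partly from bowel preparation could then be reported as a radiation effect and carried into later work, since section 2.8 presents these results as preliminary data.

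The matter is worth settling before collection. Section 9.1 stores the specimens and runs the sequencing after all of them are in. A collection time that was neither fixed nor noted cannot be recovered then.

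**Working it through.** The plan gives no figure for the microbiome analysis, so there is none to reproduce. The check sets the sections side by side, counts exposures, and asks what the planned contrasts can identify.

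**1. Instructed enemas by fraction 5** (section 5.2). One before planning CT plus one before each of five fractions: 1 + 5 = 6.

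**2. What lies between the two samples.** The Pre-Study stool may come before the planning-CT enema (0 enemas) or after it (1). The Fx 5 stool may come before that day's enema (1 + 4 = 5) or after it (6). The within-patient difference in instructed enemas is therefore between 5 − 1 = 4 and 6 − 0 = 6, depending on timing that the plan leaves open.

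**3. Time from last enema to the Fx 5 stool.** Section 5.5 has 2-3 fractions a week, or one a week at the physician's discretion. A stool given before the Fx 5 enema follows the previous one by about 7/3 = 2.3 to 7/2 = 3.5 days on average, or about 7 days with weekly treatment. A stool given after the Fx 5 enema may follow it by hours. The interval can thus run from hours to about a week.

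**4. What the contrasts identify.** Code each sample by intercept, radiation received (0/1) and current enema course (0/1), with baseline taken before any enema:

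| Sample | Intercept | Radiation | Enema course |
|---|---|---|---|
| Baseline | 1 | 0 | 0 |
| End of radiation | 1 | 1 | 1 |
| 3-6 months | 1 | 1 | 0 |

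- First two rows only: the radiation and enema columns are identical, so the rank is 2 for 3 parameters. The change estimates (radiation effect + enema effect). More patients do not alter this.
- All three rows: the determinant is 1 × (1×0 − 1×1) = −1, which is not zero, so the rank is 3. This holds only if the radiation effect is assumed to be the same at 3-6 months as at the end of treatment and no enema effect persists. Neither assumption is stated or supported in the documents.

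**5. Reach.** The primary endpoints (feasibility and acute GI/GU toxicity) and the secondary endpoints (EPIC and AUA) do not use stool.

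**The case against.** The strongest reply is that the stakes are low and the confounding is not total. Sampling is optional, the analysis is labelled exploratory, and no test, threshold or decision depends on it. The lack of an unirradiated comparison is an ordinary limit of a single-arm correlative study, and nothing in the documents says that an enema alters stool flora. All of this stands, and it is why the point is minor.

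A reader might also infer more than the documents support:

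- *That radiation and enemas start and stop together, with the same exposure in every patient.* They do not. The planning-CT enema precedes any radiation. The schedule's footnote allows nodal treatment over 5-6 weeks, while section 5.2 ties enemas to SBRT treatments. Fraction spacing varies under section 5.5.
- *That no later adjustment is possible.* Section 5.3.2 requires rectal dose constraints to be checked for each plan, and spacer use is optional, so rectal dose can differ between patients. Relating microbiome change to rectal dose would be imprecise with at most 30 optional donors, but it is not ruled out. The three-sample coding above also has full rank under its assumptions.
- *That section 9.1 applies its normal-versus-irradiated wording to the Fx 5 contrast.* It attaches that wording to no time point. Baseline against 3-6 months fits it equally well, and section 2.8 covers the period after radiotherapy as well as during it.
- *That correlations with immune markers must be contaminated.* If every patient's change were shifted by the same constant c, then corr(d + c, m) = corr(d, m). Only an enema effect that varies between patients could disturb the correlation.
- *That enema timing will go unrecorded.* The protocol does not ask for it, but the case report forms are not in the documents.

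None of these removes the core point. The simple change from baseline to end of radiation combines two exposures, and the plan interprets it as one.

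**Conclusion.** The point holds in a limited form. As planned, the simple baseline to end-of-radiation change measures radiation plus bowel preparation, with 4 to 6 more instructed enemas behind the second sample than behind the first, and it should not be described as the effect of radiation alone. The baseline to 3-6 month change is free of this concurrent exposure. It remains uncontrolled, however, and it does not answer the question about change during treatment.

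This rests on patients following the instruction in section 5.2 and on the Fx 5 timing in the schedule. The size of any enema effect is unknown from the documents, so the possible bias has no figure. No primary or secondary endpoint is touched. Severity: minor.

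**What to change.** Leave the bowel preparation as it is, and amend section 9.1 and the schedule in section 5:

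1. Collect the baseline stool before the planning-CT enema.
2. Collect the end-of-radiation stool at one set interval relative to the last enema, the same for all donors, and record the time of the last enema for each sample. Home collection is already allowed, which makes this practical.
3. Describe the baseline to end-of-radiation contrast as radiation plus bowel preparation. Report baseline to 3-6 months alongside it as the contrast free of concurrent protocol enemas.

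Items 1 and 2 make the samples comparable between patients; they do not separate the two exposures. Item 3 deals with attribution.

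The cost is a few lines of wording and one case report form field, if the form does not already have it. Some timed samples may come late or be missed, and the on-treatment claim becomes narrower.

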12.2 Sample Size/Accrual Rate

We plan to accrue 30 patients over 3 years, or about 5 patients every 6 months. Using an exact Clopper-Pearson binomial two-sided interval, we will be able to estimate the proportion of treatments that are feasible (comply with treatment plan) to within +/- 16%. This estimation conservatively assumes a 50% feasibility rate, leading to a 95% confidence interval from 31.3% to 68.7%.

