12.4 Analysis of Primary and Secondary Endpoints

Primary Endpoint:

The first primary endpoint of feasibility will be measured by the percentage of treatments that are delivered according to plan. The count and percent will be tabulated, and a 95% confidence interval estimated using an exact Clopper-Pearson binomial two-sided interval.

The second primary endpoint of safety will be measured by the percentage of treatments that do not lead to a GI/GU adverse event (defined as >Grade 3) within 30 days of treatment. The count and percent will be similarly tabulated, and a 95% confidence interval estimated using an exact Clopper-Pearson binomial two-sided interval.

Finally, the proportion of patients for whom the treatment was feasible and safe will be tabulated, and a 95% confidence interval estimated using an exact Clopper-Pearson binomial two-sided interval.

Planned sub-group analyses include feasibility, safety, and combination of both within each of the four potential target dose levels (37.5, 40, 42.5 or 45 Gy).

Secondary Endpoints:

HRQOL measures at baseline and at follow up (3-6 months post treatment start) will be summarized numerically and graphically using mean (sd), median (interquartile range), or count (percent) as appropriate, and 95% confidence intervals estimated where possible. Changes in scoring from pre- to post-treatment will also be similarly studied. EPIC overall scores as well as domain summary scores (urinary incontinence, urinary irritative/obstructive, bowel, sexual, hormonal) and individual item responses will be studied. Similarly, overall score as well as individual item responses will be studied for the AUA symptom survey.

13 Data and Safety Monitoring Plan (DSMP)

The WCMC Data and Safety Monitoring Committee (DSMC) is the central monitoring board for this study.

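### The ±16% precision given for feasibility with 30 patients is wrong: the plan's own 95% interval of 31.3% to 68.7% is ±18.7 percentage points

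*Combined protocol and SAP*

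**What the plan says.** Section 12.2 (Sample Size/Accrual Rate) sets the sample size: "We plan to accrue 30 patients over 3 years". It then describes the precision this gives for the first primary endpoint, feasibility. The method is named ("Using an exact Clopper-Pearson binomial two-sided interval"), and the claim is that the trial can "estimate the proportion of treatments that are feasible (comply with treatment plan) to within +/- 16" percent.

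The next sentence gives the basis for that claim. "This estimation conservatively assumes a 50% feasibility rate", it says, "leading to a 95% confidence interval from 31.3% to 68.7" percent.

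Section 12.4 plans the same method and level for the analysis of feasibility: "a 95% confidence interval estimated using an exact Clopper-Pearson binomial two-sided interval".

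Section 12.2 contains no hypothesis test, power calculation or target feasibility rate.

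**The concern.** The printed interval is symmetric about 50%, so its margin can be read directly as half its width. That margin is 18.7 points, while the preceding sentence says 16. The second sentence refers back to the same estimation, so the two figures cannot both be right.

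The precision statement is the only quantitative support for enrolling 30 patients. Because the 50% rate is described as conservative, a reader will take 16 points as the worst case. If 16 is wrong, the plan promises more precision than the design delivers.

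**Working it through.** **Inputs**

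| Input | Value | Source |
|---|---|---|
| Sample size, n | 30 | Section 12.2 |
| Assumed feasibility rate | 50%, so x = 15 | Section 12.2 |
| Method | Exact Clopper-Pearson, two-sided | Sections 12.2 and 12.4 |
| Confidence level | 95% | Sections 12.2 and 12.4 |
| Stated interval | 31.3% to 68.7% | Section 12.2 |
| Stated margin | ±16% | Section 12.2 |

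**Step 1: reproduce the stated interval.** With α = 0.05, the Clopper-Pearson limits are beta quantiles:

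- Lower limit = the α/2 quantile of Beta(x, n − x + 1) = the 0.025 quantile of Beta(15, 16) = 0.3130
- Upper limit = the 1 − α/2 quantile of Beta(x + 1, n − x) = the 0.975 quantile of Beta(16, 15) = 0.6870

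This is 31.3% to 68.7%, as printed.

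**Step 2: margin of that interval.** (68.70 − 31.30)/2 = 18.70 percentage points. The distance from 50% is 18.7 on each side. The stated 16% is not reproduced.

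**Step 3: could another method or level give 16 at 15/30?**

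| Method | Level | Half-width (points) |
|---|---|---|
| Clopper-Pearson | 95% | 18.7 |
| Wald, 1.96 × √(0.25/30) | 95% | 17.9 |
| Wald with continuity correction, adding 1/60 | 95% | 19.6 |
| Wilson (Agresti-Coull is identical here) | 95% | 16.8 |
| Jeffreys | 95% | 17.2 |
| Mid-P | 95% | 17.5 |
| Clopper-Pearson | 90% | 16.1 (33.9% to 66.1%) |
| Clopper-Pearson | 80% | 13.0 |

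None of the 95% methods tried gives 16. The 90% Clopper-Pearson interval does after rounding.

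**Step 4: could another feasibility rate give 16 with n = 30 at 95%?** Away from 50% the exact interval is asymmetric, so both the average half-width and the longer (lower) arm are shown.

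| Feasible | 95% Clopper-Pearson | Half of width | Lower arm |
|---|---|---|---|
| 15/30 | 31.3% to 68.7% | 18.7 | 18.7 |
| 23/30 | 57.7% to 90.1% | 16.2 | 18.9 |
| 24/30 | 61.4% to 92.3% | 15.4 | 18.6 |
| 27/30 | 73.5% to 97.9% | 12.2 | 16.5 |
| 28/30 | 77.9% to 99.2% | 10.6 | 15.4 |

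An average half-width near 16 appears at about 23/30, which is not the 50% that the plan assumes.

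**Step 5: what n would give 16 at 50% and 95%?** The half-width is 16.20 at n = 40 (20/40), 15.99 at n = 41 (20/41 or 21/41) and 15.81 at n = 42 (21/42). About 41 patients would be needed.

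**The case against.** The strongest reply is that little depends on the figure. The correct interval is printed in the very next sentence, so a reader who uses it is not misled. Section 12.2 states what 30 patients will deliver; it does not say that 30 was derived from a 16-point requirement. The analysis in section 12.4 uses the observed counts and is unaffected. This stands, and it limits the point to a text correction: the 41-patient figure measures the size of the discrepancy and should not be read as a shortfall of 11 patients.

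A second reply is that 50% is the worst case, and that at 24/30 or better the average half-width is already below 16 points. This is true, but it does not rescue the sentence, which ties its margin to the 50% rate. It also helps less than it seems to: the arm below the estimate is still 18.6 points at 24/30, and drops below 16 only at 28/30 or more. The document gives no expected feasibility rate, so these are illustrations and not predictions.

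Third, the 90% explanation is conjecture, since no 90% level appears anywhere in the document. That is so. The correction does not rely on it, because sections 12.2 and 12.4 both specify 95%.

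**Conclusion.** The concern holds. The interval in section 12.2 is right for its stated inputs, and the ±16% is wrong. The margin at a 50% rate with 30 patients is ±18.7 percentage points: 2.7 points more than stated, or about 17% wider (18.7/16 = 1.17).

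The conclusion rests only on the plan's own inputs: 30 patients, a 50% rate, a 95% level and the exact Clopper-Pearson method. The error should be corrected because it sits in the sole quantitative justification of the sample size and contradicts the sentence that follows it. It does not invalidate the design or the planned analysis.

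**What to change.** In section 12.2, replace the 16% margin with ±18.7 percentage points (or within about 19 percentage points). Keep 30 patients and the interval of 31.3% to 68.7%.

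Optionally, add the interval at a high feasibility rate, for example 73.5% to 97.9% at 27/30, to show the precision and the asymmetry away from 50%.

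The cost is one number in the protocol and a slightly less favourable precision statement. Enrolment and analysis stay as they are. If the sponsor did intend 16 points at 95% confidence as a requirement, the plan should say so and revisit the sample size.

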12.3 Stratification Factors

Patients will not be risk-stratified.

12.4 Analysis of Primary and Secondary Endpoints

Primary Endpoint:

The first primary endpoint of feasibility will be measured by the percentage of treatments that are delivered according to plan. The count and percent will be tabulated, and a 95% confidence interval estimated using an exact Clopper-Pearson binomial two-sided interval.

The second primary endpoint of safety will be measured by the percentage of treatments that do not lead to a GI/GU adverse event (defined as >Grade 3) within 30 days of treatment. The count and percent will be similarly tabulated, and a 95% confidence interval estimated using an exact Clopper-Pearson binomial two-sided interval.

Finally, the proportion of patients for whom the treatment was feasible and safe will be tabulated, and a 95% confidence interval estimated using an exact Clopper-Pearson binomial two-sided interval.

Planned sub-group analyses include feasibility, safety, and combination of both within each of the four potential target dose levels (37.5, 40, 42.5 or 45 Gy).

Secondary Endpoints:

HRQOL measures at baseline and at follow up (3-6 months post treatment start) will be summarized numerically and graphically using mean (sd), median (interquartile range), or count (percent) as appropriate, and 95% confidence intervals estimated where possible. Changes in scoring from pre- to post-treatment will also be similarly studied. EPIC overall scores as well as domain summary scores (urinary incontinence, urinary irritative/obstructive, bowel, sexual, hormonal) and individual item responses will be studied. Similarly, overall score as well as individual item responses will be studied for the AUA symptom survey.

13 Data and Safety Monitoring Plan (DSMP)

The WCMC Data and Safety Monitoring Committee (DSMC) is the central monitoring board for this study.

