1.1 Primary Objectives

1.1.1 Determine the feasibility and safety of delivering SBRT w/SIB without increased acute G3 GI/GU toxicity.

Feasibility is defined as a plan meeting treatment planning objectives and normal tissue constraints. Specifically the dose distribution of the MRI-guided technique, will be assessed with regard to fulfilling protocol requirements of: a) coverage of the planning target volume (PTV) , b) constraints to organs at risk (OAR) by dose volume histogram (DVH) analysis and whether this can be done through standard set-up techniques or non-invasively through MRI based planning, c) coverage of high-risk prostate nodules. The total dose delivered (either 37.5, 40, 42.5 or 45 Gy mean dose to the contoured nodule) will be determined by selecting the plan with the highest dose to visible nodules while maintaining normal tissue constraints to the urethra and rectum. We will track the number of treatment plans for each dose level (37.5, 40, 42.5 or 45 Gy) that can be delivered while planning objectives.

Safety of this approach will be determined by assessing acute GI/GU toxicity (CTCAE 4.0 criteria). Treatment will be deemed safe if there is no acute >G3 GI/GU toxicity within the first 30 days of treatment (CTCAE 4.0 criteria). Given that the treatment plans will meet standard normal tissue constraints used for prostate SBRT, we do not anticipate any increased toxicity on this study compared to standard prostate SBRT.

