2.6 ViewRay: a unique radiation delivery approach

The ViewRay MRIdian Linac system is a radiation delivery machine that integrates a linear accelerator with real-time MRI imaging. The ViewRay machine allows fusion of MR imaging with treatment planning. The uniqueness of this approach is the image guided delivery component, based on precise MRI-based detection of target and normal tissue during treatment in real-time. The ViewRay will provide real-time MRI imaging to ensure that the high-dose region is precisely targeted. MRI guided radiation has the benefit of not requiring fiducial implantation or excess radiation exposure from multiple cone beam CT. Furthermore, motion monitoring can be

performed with images acquired up to 4 frames a second, allowing live feedback of treatment position.

ViewRay offers the ideal system for delivery of prostate SBRT, due to its ability to provide image guidance “live”, during treatment. Real-time MRI imaging allows superior soft-tissue differentiation with excellent visualization of the prostate. This ViewRay platform offers the ideal setting for this study, that aims at precisely delivering prostate SBRT with a simultaneous integrated boost to visible nodules.

The goal of this study is to assess feasibility and safety of using the ViewRay to deliver prostate SBRT with SIB. Feasibility is defined as the ability to deliver treatment as planned (within the constraints defined in Section 5.3 Radiation Planning) and safety is defined as lack of acute G3 GI or GU toxicity within 30 days. The proposed SBRT dose (35-36.25 Gy in 5 fractions to the whole prostate) has been reported in the literature to be safe and well tolerated (Table 2), with no acute G3 toxicity. The proposed boost dose of an additional 0.5, 1.0, 1.5 or 2 Gy per fraction (total dose 37.5-45 Gy, depending on normal tissue constraints) is within the range of current standard of care SBRT doses, and is expected to be well-tolerated if normal tissue constraints are met. By applying rigorous normal tissue constraints and capitalizing on the imaging capability of the ViewRay we plan to deliver a treatment that is non-invasive and exceptionally precise.

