10 MEASUREMENT OF EFFECT

This is a feasibility study. Feasibility will be achieved if a treatment plan can be achieved with the parameters described below:

Specifically the treatment must fulfill all three aspects of a) coverage of the prostate PTV as defined in 5.3 to dose of 35 Gy in 5 fractions, b) no more than acceptable radiation dosage to organs at risk (OAR) by DVH analysis (refer to section 5.3), and c) full coverage of high-risk prostate nodules, as defined by mean dose to contoured nodules. The total mean dose to be delivered (either 37.5, 40, 42.5 or 45 Gy) will be determined by selecting the plan with the highest dose to visible nodules while maintaining normal tissue constraints. The first primary endpoint will be degree of feasibility, as measured by the percentage of treatments that are delivered according to plan.

Safety of this approach will be determined by assessing acute GI/GU toxicity (CTCAE 4.0 criteria). Treatment will be deemed safe if there are no acute greater than grade 3 GI/GU adverse events within the first 30 days of treatment (CTCAE 4.0 criteria). The second primary endpoint will be safety, as measured by the percentage of treatments that are delivered without GI/GU toxicity within the first 30 days from start of treatment. Given that the treatment plans will meet standard normal

tissue constraints used for SBRT, and rigorous safety metrics need to be met before radiation is delivered, we do not anticipate any increased toxicity on this study compared to standard SBRT.

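### Feasibility, the first primary endpoint, is defined at planning in some sections and at delivery in others, and no section says how to count a patient with no achievable boost plan

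*Combined protocol and SAP*

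**What the plan says.** **Feasibility at planning.** Section 1.1 states: "Feasibility is defined as a plan meeting treatment planning objectives and normal tissue constraints". The Protocol Summary has the same sentence. Section 10 opens in the same sense: "Feasibility will be achieved if a treatment plan can be achieved with the parameters".

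**Feasibility at delivery.** Section 2.6 states: "Feasibility is defined as the ability to deliver treatment as planned". Section 12.4 states: "The first primary endpoint of feasibility will be measured by the percentage of treatments that are delivered according to plan". The sentences that name the first primary endpoint in sections 10 and 12.1.1 use this delivery measure too.

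**A blend.** Section 12.1.1 defines feasibility as a plan that fulfils the plan fixed before treatment starts. It then lists criteria (a) to (c): target coverage, organ doses by DVH, and mean nodule dose. It ends with the delivery measure.

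**Unit and denominator.** Section 12.2 speaks of treatments: "we will be able to estimate the proportion of treatments that are feasible (comply with treatment plan) to within +/- 16". For the combined endpoint, section 12.4 speaks of patients: "the proportion of patients for whom the treatment was feasible and safe will be tabulated". No analysis population is defined.

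**Who reaches treatment.** Under 5.3.2 and 10, the boost level is the highest of the four that respects the normal tissue limits. Section 10 adds that safety metrics have to be satisfied before radiation is given. The subgroups in 12.4 are the four dose levels and nothing else.

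**The concern.** This is a single-arm feasibility study, and this percentage is the first of its two primary results. If planning and delivery are both called feasibility, a reader cannot tell what the reported rate means, and two analysts could compute different rates from the same data.

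The gap matters most for the patient whose anatomy allows none of the four boost levels. Under 1.1 he is the clearest case of infeasibility. Under 12.4 he has no stated place: he may never have a protocol treatment to count, and no dose-level subgroup fits him. If he is left out, the patients who remain are those whose plans already met the limits, and the rate moves towards 100%. Because the text does not settle this, the denominator could be chosen after the results are known.

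**Working it through.** **1. The plan's own figure.** Section 12.2 gives "This estimation conservatively assumes a 50% feasibility rate, leading to a 95% confidence interval from 31.3% to 68.7"%. The inputs are n = 30 (12.2) and x = 15 (50% of 30). The exact Clopper-Pearson limits are: lower = the 0.025 quantile of Beta(x, n − x + 1); upper = the 0.975 quantile of Beta(x + 1, n − x). With Beta(15, 16) and Beta(16, 15), the result is 31.3% to 68.7%, as stated. So the sample size section applies its rate to all 30 patients. (The half-width is (68.7 − 31.3)/2 = 18.7 points, not the 16 stated in the same section. That is a separate matter.)

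**2. How each definition classifies a patient.**

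| Patient | Planning definition (1.1, opening of 10) | Delivery measure (2.6, 12.4) |
|---|---|---|
| Acceptable plan, delivered to plan | feasible | feasible |
| Acceptable plan, delivery deviates | feasible | not feasible |
| No acceptable plan at any of the four levels | not feasible | no rule |

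The definitions agree only in the first row.

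**3. Size of the denominator question.** Let k be the number of the 30 patients with no acceptable boost plan, and let all others be treated to plan. The documents give no value for k, so a range is shown. Reading A counts treated patients only: (30 − k)/(30 − k). Reading B counts everyone: (30 − k)/30. Intervals are exact 95%. When x = n, the lower limit is 0.025^(1/n); for example, 0.025^(1/27) = 87.2%.

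| k (assumed) | Reading A | Reading B |
|---|---|---|
| 0 | 30/30 = 100% (88.4 to 100) | 30/30 = 100% (88.4 to 100) |
| 1 | 29/29 = 100% (88.1 to 100) | 29/30 = 96.7% (82.8 to 99.9) |
| 3 | 27/27 = 100% (87.2 to 100) | 27/30 = 90.0% (73.5 to 97.9) |
| 6 | 24/24 = 100% (85.8 to 100) | 24/30 = 80.0% (61.4 to 92.3) |

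**4. Both ambiguities together.** Assume k = 6 and 2 delivery deviations among the 24 treated. Three rates can then be defended from the same data:
- planning definition over all patients: 24/30 = 80.0% (61.4 to 92.3);
- delivery over treated patients: 22/24 = 91.7% (73.0 to 99.0);
- delivery over all patients: 22/30 = 73.3% (54.1 to 87.7).

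**5. What counts as delivered to plan.** Criteria (a) to (c) in 10 and 12.1.1 are coverage, DVH and mean-dose quantities, that is, properties of a plan. No section says what would make a delivered course depart from its plan, so the second row of the table in step 2 cannot be scored by a stated rule.

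**The case against.** The strongest reply is that the protocol nowhere restricts the denominator to treatments actually given. In 12.4, delivery to plan describes the numerator, and the denominator is simply treatments. The only worked use of that word, in 12.2, takes it over 30 patients: "We plan to accrue 30 patients over 3 years, or about 5 patients every 6 months". The combined endpoint is a proportion of patients. Nor does any section say that a patient without an acceptable boost plan goes untreated or leaves the analysis. The Protocol Summary calls prostate SBRT standard of care, so he might be treated without the boost and count as a treatment not to plan. The Protocol Summary and 1.1 also promise to track how many plans can be delivered at each level, so a shortfall against 30 would show. Finally, no feasibility threshold is set, so no formal decision turns on the rate.

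Most of this stands. A reader might infer that 12.4 removes unplannable patients by rule and so biases the rate towards 100%. The documents do not support that: it follows from one reading, and 12.2 points to the other. A reader might also infer from the study calendar, which lists only toxicity assessment and optional samples during the fractions (at fraction 5), that delivery failures go unmeasured. That does not hold either. Section 12.4 measures delivery, and 11.1 says all treatment data are captured for all enrolled patients. What is missing is the scoring rule, not the data.

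The reply does not remove the conflict between the definitions. The 30 in 12.2 is planned accrual, not a rule for counting unplannable patients, and the tracking by level counts plans that succeed.

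**Conclusion.** The point holds as an inconsistency and an omission in the first primary endpoint. Feasibility has two incompatible definitions, the unit shifts within 12.4, the patient with no achievable boost plan has no stated classification, and delivery to plan has no criterion.

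The numerical effect depends on an assumed count. It is nil if every patient has an acceptable plan. Otherwise, with all others treated to plan, the two readings differ by k/30: 3.3 points for one patient, 10 for three, 20 for six. Exclusion of such patients is a risk that the wording permits, not a rule that it states, and its likelihood cannot be judged from the documents. The plan still needs correcting, because the main result of a feasibility study should not depend on which section the analyst follows.

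**What to change.** Use one per-patient definition in the Protocol Summary and in 1.1, 2.6, 10, 12.1.1 and 12.4:

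- **Denominator:** all registered eligible patients.
- **Feasible:** a plan at one of the four boost levels meets criteria (a) to (c), and all 5 SBRT fractions are delivered according to the plan set before the start of treatment. State what counts as a departure from that plan.
- **Not feasible:** any other patient, expressly including one with no acceptable boost plan. Tabulate the reasons, so that withdrawal before planning can be told apart from planning failure.
- **Also report separately:** plan achievability and delivery to plan, each with its exact 95% interval.
- **Combined feasible-and-safe proportion:** use the same denominator.
- **Dose-level tables:** add a row for no achievable level.

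Take delivery status for each fraction from the existing treatment record. The cost is wording in these sections, a few case report form fields and a feasibility rate that may look less favourable. No patients or procedures are added. The change concerns counting in the analysis only and alters no dose or clinical rule.
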